Musculoskeletal injury is a significant global health concern, with injury contributing to large amounts of patient pain, disability, and a decrease in overall wellbeing [1]. Emerging areas of research and treatment in orthopedic injuries using stem and progenitor cells have shown great potential. Stem cells are biological cells which differentiate into many types of human tissue. Stem cells differentiate into specific cell lineages to manage healthy tissues and cells, as well as repair damaged tissues and cells. Stem cells can specialize into progenitor cells, which have gone one step further toward a specific differentiation pathway. Progenitor cells then change according to the given environment (i.e., growth factors, stress) and perform specific cellular functions. Progenitor cells are found in many tissues, including the peripheral blood and bone marrow. Progenitor cells act as important repair cells for the musculoskeletal system, specifically for bone and cartilage [1]. These progenitor cells are mobilized and activated to the peripheral blood circulation during episodes of stress, injury, and exercise [2, 3]. Cell therapies using progenitor cells have shown great potential for addressing acute, chronic, and traumatic orthopedic injury.

One cell therapy of interest currently involves bone marrow aspiration and concentration. Bone marrow aspiration and concentration is a method of progenitor cell harvest. Orthopedic surgeons have begun to augment surgical procedures and treat degenerative conditions such as osteoarthritis and cartilaginous injury with injections of concentrated bone marrow aspirate (cBMA) [4-8]. The use of cell therapies may contribute to decreased recovery time and morbidity rates [9-11]. Hernigou et al. showed significant improvement in patient outcomes could be achieved by the use of cBMA as an adjunct therapy in standard of care rotator cuff repair (RCR) [5]. In clinical application, studies have suggested that the success of these treatments is dependent on the total quantity and utility of harvested progenitor cells [5,7]. While bone marrow aspiration is frequently utilized for orthopedic point of care applications, the number of progenitor cells harvested is variable and dependent on body mass, aspiration technique, and location of harvest [5, 12]. Optimizing the harvest procedure is a key step in the development of bone marrow aspirate for orthopedic applications. Studies have attempted to find the most appropriate locations for harvesting bone marrow aspirate [13-17]. The preferred site for bone marrow extraction is the posterior iliac spine [13-17]. The posterior iliac spine yields the greatest concentration of viable nucleated cells when compared to the anterior iliac spine [13]. The posterior iliac spine also yields a greater concentration of nucleated cells when compared to other appendicular osseous sites, including the distal femur, proximal tibia, distal tibia, calcaneus, and proximal humerus [13-16]. In one study, the cBMA harvested from the posterior superior iliac spine (PSIS) resulted in a 3.0 times greater cellular yield and an 8.3 times greater proliferative cell product than cBMA from the proximal humerus [17]. Determining the quantity of progenitor cells in these samples can provide clinicians with a more cost-effective alternative for harvesting progenitor cells that can be used for surgical augmentation. However,

the potential for progenitor cells to be harvested from the diaphysis of the humerus (deep humerus) has yet to be quantified. Thus, this the aim of this study is to analyze the cellular characteristics of cBMA from two extraction sites (PSIS and deep humerus) from patients undergoing standard-of-care arthroscopic rotator cuff repair surgery. Additionally, we aim to determine if patient positioning during PSIS harvest has any effect on the cellular content of collected cBMA.

2 Study Design

This is a single site, comparative quantitative analysis study of the cellular characteristics of bone marrow aspirate from two extraction sites (PSIS and deep humerus) from patients undergoing standard-of-care arthroscopic rotator cuff repair surgery. 30 total patients will be recruited through the Andrews Institute physician practices. Potential participants will be prescreened for inclusion and exclusion criteria through standard of care medical evaluations. Once a potential participant has agreed to be involved in the study, they will go through the described informed consent process. Patients meeting the inclusion criteria will have the study explained to them by one of the members of the research team, and they will be given an opportunity to participate if they are interested. No specific advertising or recruitment material will be utilized.

After the described screening and informed consent process have been completed, all participants will undergo standard-of-care arthroscopic rotator cuff repair surgery. During all surgeries, bone marrow will be aspirated from the PSIS and from the deep humerus. The first 15 participants will have bone marrow aspirated from the PSIS while in the prone position on the operating table. The final 15 participants will have bone marrow aspirated from the PSIS while in the lateral decubitus position on the operating table. Both cohorts will undergo deep humeral harvest intraoperatively in the lateral decubitus position. One mL of cBMA from each harvest site from each surgery will be removed and sent to the AREF Regenerative Medicine Center (RMC) for analysis. The remaining cBMA will be used to augment the rotator cuff repair surgery.

3 Objectives

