3.2 Secondary Objective

The secondary objective is to determine if prone verses lateral decubitus participant positioning influences the quantity of harvested cells from the PSIS.

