3.4 Secondary Effectiveness Endpoints

The secondary effectiveness endpoints of this study include cellular content measures of cBMA collected from each anatomical position (as outlined in section 6.2).

4 Hypotheses

4.1 Null Hypothesis:

H_0 - Participants will have similar cellular content (*in vitro*) in bone marrow aspirate taken from the PSIS and from deep humeral harvest. Additionally, patient positioning will not affect the cellular content of bone marrow from the PSIS.

4.2 Alternative Hypothesis:

H_1 - Participants will not have similar cellular content (*in vitro*) in bone marrow aspirate taken from the PSIS and from deep humeral harvest. Additionally, patient positioning will affect the cellular content of bone marrow from the PSIS.

5 Participant Recruitment and Screening

5.1 Screening Process:

Once interested participants are identified and prescreened, a screening visit will be scheduled (visit 1). During the screening visit, a screening form will be completed which includes the inclusion and exclusion criterion below. If an individual answers "yes" to any of the initial screening exclusion questions, they will be informed that they do not qualify for the study, and they will be informed that they can keep their screening form and their medical care will not be adversely affected by not enrolling in the study. If all answers are "no" then the form will be placed in the study documents and the enrollment process will continue.

5.1.1 Inclusion Criteria:

- 18-80 years of age
- Diagnosis of a rotator cuff tear requiring arthroscopic rotator cuff repair

5.1.2 Exclusion Criteria:

- Patients who require superior capsular reconstruction or revision rotator cuff repair
- Diabetes
- Immune disorders

- Past medical history of a metastatic or other cancer which required chemotherapy/radiation therapy
- Rheumatoid arthritis
- Is unable to comprehend the study documents or give informed consent

Once the screening requirements are met, the informed consent form will be provided to the participant on paper or electronically via REDCap for review ensure the volunteer understands the details of the study including the benefits and risk factors. The subject will be provided sufficient time to consent and sign the informed consent form (ICF). The principal investigator (PI) and study/research team will be available to answer any questions or provide clarifications during the informed consent process.

5.2 Informed Consent 21 CFR 50

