7.4 AE & SAE Collection and Reporting

Throughout the study the research team will monitor the occurrence of AE and SAE. Data will be collected if an instance occurs, and the PI will be notified. All AE data, such as onset date, resolution date, outcome and treatments given will be documented in the source documents and will be recorded in the EDC and analyzed for severity to follow reporting protocol if severity level.

Follow-up will occur using the provided safety monitoring form if AE occurs. The follow up will end either when the symptoms resolve or up to 30 days past the end of the study participation.

7.5 Risks and Discomforts:

Standard sterile precautions for surgical procedures will be utilized for the rotator cuff repair surgery, but with any surgery there is risk of infection, bleeding, and swelling. There will also be a small needle insertion hole into the humerus and the iliac crest for the bone marrow stem cell collection, which will be about the same size as an IV insertion. This may have some minor pain or swelling and there is a very minor risk of infection. Pain post procedure can occur but is usually self-limiting. Bruising may also

occur. As with any research involving patients there is the inherent risk of a breach in patient confidentiality though this will be minimized using participant code numbers and adherence to all HIPAA guidelines.

8 Data Management Procedures

All personal information is strictly confidential, and no names will be disclosed except as required by law. Data from cellular analysis and demographics will be compiled in Microsoft Excel. The spreadsheet will not contain protected health information as all compiled data will be de-identified. The spreadsheet will be stored in a secure password protected folder on a laptop that only the study Investigators will have access to and will be permanently deleted following publication of any and all manuscripts, if any, written as a result of this research. Records related to this study will be securely retained in a secure location for a period of 3 years after the completion of the study or longer as required by law. At that time, all records will be properly destroyed.

9 Data Analysis

A combination of Excel and SAS Studio (Version 3.8 on SAS 9.4, SAS Institute Inc., Cary, NC) will be used for data analysis. All compiled data will be de-identified.

10 Statistical Considerations

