Descriptive statistics will be compiled for all numeral measures (Demographics, CBC, TNC, viability, CFU-F). Data will be analyzed for differences between experimental groups (PSIS v. deep humeral harvest, Prone vs. lateral decubitus positions) using 1-Way ANOVA and appropriate post-hoc analysis procedures (ex: Tukey's Honestly Significant Difference (HSD)). A significant p-value of < 0.05 for rejecting the null hypothesis will be used for all measures.

11 Quality Control and Assurance

All protocols will be monitored and analyzed data will be checked for accuracy by the principal investigator and /or a designated AREF research team member. All medical data will be kept in compliance with HIPAA guidelines.

12 References

1. Akpancar, S., et al., *The Current Perspectives of Stem Cell Therapy in Orthopedic Surgery*. Arch Trauma Res, 2016. **5**(4): p. e37976.
2. Marycz, K., et al., *Endurance Exercise Mobilizes Developmentally Early Stem Cells into Peripheral Blood and Increases Their Number in Bone Marrow: Implications for Tissue Regeneration*. Stem Cells Int, 2016. **2016**: p. 5756901.
3. Rochefort, G.Y., et al., *Multipotential mesenchymal stem cells are mobilized into peripheral blood by hypoxia*. Stem Cells, 2006. **24**(10): p. 2202-8.
4. Hauser, R.A. and A. Orloffsky, *Regenerative injection therapy with whole bone marrow aspirate for degenerative joint disease: a case series*. Clin Med Insights Arthritis Musculoskelet Disord, 2013. **6**: p. 65-72.
5. Hernigou, P., et al., *Biologic augmentation of rotator cuff repair with mesenchymal stem cells during arthroscopy improves healing and prevents further tears: a case-controlled study*. Int Orthop, 2014. **38**(9): p. 1811-8.
6. Hernigou, P., et al., *Cell therapy of hip osteonecrosis with autologous bone marrow grafting*. Indian Journal of Orthopaedics, 2008. **43**(1): p. 40-45.
7. Hernigou, P., et al., *Percutaneous autologous bone-marrow grafting for nonunions*. Journal of Bone and Joint Surgery, 2005. **87**(7): p. 1430-1437.
8. Saw, K.Y., et al., *Articular cartilage regeneration with autologous peripheral blood stem cells versus hyaluronic acid: a randomized controlled trial*. Arthroscopy, 2013. **29**(4): p. 684-94.
9. Vangsness, C.T., Jr., H. Sternberg, and L. Harris, *Umbilical Cord Tissue Offers the Greatest Number of Harvestable Mesenchymal Stem Cells for Research and Clinical Application: A Literature Review of Different Harvest Sites*. Arthroscopy, 2015. **31**(9): p. 1836-43.

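### The prone-versus-lateral comparison makes no use of body mass, which the protocol itself names as a determinant of cell yield and does not list as a data item

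*Protocol*

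**What the plan says.** - **Determinants of yield.** The protocol's introduction states that "the number of progenitor cells harvested is variable and dependent on body mass, aspiration technique, and location of harvest". It gives no size or direction for body mass.
- **Secondary question.** Section 3.2: "The secondary objective is to determine if prone verses lateral decubitus participant positioning influences the quantity of harvested cells from the PSIS".
- **Allocation.** Section 2: "30 total patients will be recruited"; then "The first 15 participants will have bone marrow aspirated from the PSIS while in the prone position on the operating table" and "The final 15 participants will have bone marrow aspirated from the PSIS while in the lateral decubitus position on the operating table". Sections 6 and 6.1 repeat this. No randomisation, matching or stratification is described.
- **Eligibility.** Section 5.1.1 sets limits by age and diagnosis, and section 5.1.2 has no exclusion for weight or BMI. At the screening visit (section 5.1), "a screening form will be completed which includes the inclusion and exclusion criterion below".
- **Data.** Section 8: "Data from cellular analysis and demographics will be compiled in Microsoft Excel". The demographic items are not listed there or elsewhere.
- **Analysis.** Section 10 plans descriptive statistics for demographics and the cellular measures. It then compares harvest sites and positions, the latter as "Prone vs. lateral decubitus positions) using 1-Way ANOVA" with post-hoc tests. No covariate is named.

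**The concern.** Of the three determinants that the protocol names, two are dealt with by design. Location is the factor under study, and section 6.1 fixes the needle, syringes, volumes and processing setting. Body mass is left free: eligibility does not restrict it, allocation does not balance it, and the stated analysis does not use it.

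This matters little for the primary comparison of PSIS with deep humerus, because both samples come from the same patient. It matters for the position comparison, where each patient contributes to one position only. Two distinct things are at stake:

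- **Bias.** Position follows enrolment order. If the body mass of the patients coming to surgery changes over the recruitment period, the change enters the position contrast and the ANOVA p-value does not allow for it.
- **Precision.** Even if enrolment order behaves like chance, variation in yield due to body mass stays in the error term of a comparison of 15 with 15.

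**Working it through.** The protocol gives no power, effect size or SD, so it has no figure of its own to reproduce.

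**Inputs.** From the protocol: n = 15 per position (section 2) and a significance level of 0.05 (section 10). Assumed: a two-sided test, 80% power for the detectable difference, and a within-cohort correlation r between body mass and a cellular measure. The documents give no r; 0.3 to 0.5 is the main range, with 0.2 shown as a lower value. Differences are in within-cohort SD units.

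**1. Imbalance in body mass if enrolment order acted like chance.**
- SE of the standardised difference = sqrt(1/15 + 1/15) = 0.365.
- 95% range = ±1.96 × 0.365 = ±0.72 SD.
- Probability of a gap above 0.5 SD = 2 × [1 − Φ(0.5/0.365)] = 0.17.

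**2. Shift in the unadjusted position contrast.** Shift = r × gap.
- Gap 0.5 SD: 0.10 (r = 0.2), 0.15 (r = 0.3), 0.25 (r = 0.5).
- Gap 0.72 SD: 0.21 (r = 0.3), 0.36 (r = 0.5).

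The SE of the contrast itself is 0.365 SD. If the gap arises by chance, these shifts are already part of that SE.

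**3. If the gap is systematic.** Suppose the two cohorts come from populations whose mean body mass differs by 0.5 SD, and position has no effect. The two-sided rejection rate (noncentral t, 28 df, noncentrality = 0.5r × sqrt(15/2)) is then, against the nominal 5%:
- 5.8% at r = 0.2
- 6.8% at r = 0.3
- 10.1% at r = 0.5

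The 0.5 SD drift is an illustration; nothing in the protocol says that it will occur.

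**4. Precision gained by adjustment.** Residual variance is multiplied by (1 − r²) and error df fall from 28 to 27. Noncentral t, body mass balanced:

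| r | Variance removed | Detectable difference, 80% power | Power for 1.0 SD |
|---|---|---|---|
| unadjusted | – | 1.06 SD | 75% |
| 0.2 | 4% | 1.04 SD | 77% |
| 0.3 | 9% | 1.01 SD | 79% |
| 0.5 | 25% | 0.92 SD | 86% |

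**5. The price of adjusting when body mass is unbalanced.** An observed gap of 0.5 SD multiplies the variance of the adjusted contrast by 1 + 0.5²/[(2/15) × 28] = 1.067. The net variance ratio against the unadjusted contrast is:
- r = 0.2: 0.96 × 1.067 = 1.02
- r = 0.3: 0.91 × 1.067 = 0.97
- r = 0.5: 0.75 × 1.067 = 0.80

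With a weak correlation and a visible imbalance, adjustment therefore buys removal of the shift and no precision.

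**The case against.** A reader might infer that body mass is never measured, and that the omission can be neither adjusted for nor checked later. The protocol does not support this. Section 8 compiles demographics and section 10 summarises them without listing the items, so weight or BMI may be among them. Patients undergoing elective surgery would also be expected to have height and weight in the pre-operative record (an assumption), from which they could be recovered. Every participant in both cohorts also gives a deep humeral sample in the same lateral position. A patient-level factor acting on marrow generally could show there as a cohort difference, although section 10 does not plan that use.

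A reader might also infer that chance imbalance between two groups of 15 invalidates the position test. It does not. Under chance allocation the ANOVA keeps its error rate, its estimate is unbiased, and the loss is one of precision only. Bias requires systematic drift between the cohorts.

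Three further objections carry weight. The size rests on an assumed correlation, and at r = 0.3 or below the gain in precision is small. The introduction speaks of progenitor cells and does not establish that body mass affects red cells, platelets or viability, which are also endpoints under section 6.2. And the choice of covariates is often left to a statistical analysis plan, which is not at hand.

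The last objection does not dispose of the point. The protocol is not silent: it fixes a model for this comparison, and that model has no place for a determinant that the protocol itself names. An analysis plan that added a covariate would depart from the stated method.

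**Conclusion.** The point holds for the analysis of the secondary objective. The protocol names body mass as a determinant of progenitor yield, assigns position by enrolment order with nothing to balance it, and specifies a one-way ANOVA that cannot use it. On measurement, the supportable statement is narrower: body mass is not named as a data item, and what counts as demographics is undefined.

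The practical size is modest and uncertain. At an assumed r of 0.3 to 0.5, the detectable difference falls from 1.06 SD to between 1.01 and 0.92 SD. Whether there is bias as well depends on a drift between cohorts that the documents neither show nor rule out. The change is worth making because it is cheap and follows from the protocol's own premise, and because with 30 patients a covariate chosen after the data are seen would be less credible. The within-patient comparison of PSIS with deep humerus is largely unaffected.

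**What to change.** - **Section 8:** list the demographic items and include height and weight, transcribed from the pre-operative record for every participant.
- **Section 10:** for the prone-versus-lateral comparison of PSIS measures, replace the one-way ANOVA with a prespecified ANCOVA containing position and body mass. Choose weight or BMI in advance; they are different quantities, and the introduction refers to body mass. Report the unadjusted result alongside.

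**Cost:** two transcribed fields and one error degree of freedom (28 to 27). No patient or procedure is added. If body mass proves weakly related to yield and unbalanced between the cohorts, the adjusted estimate may be slightly less precise than the unadjusted one.

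**Limit:** adjustment for body mass does not remove time or learning effects from assigning the first 15 patients to one position and the final 15 to the other. That weakness of the design would remain.

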After the described screening and informed consent process have been completed, all participants will undergo standard-of-care arthroscopic rotator cuff repair surgery. During all surgeries, bone marrow will be aspirated from the PSIS and from the deep humerus. The first 15 participants will have bone marrow aspirated from the PSIS while in the prone position on the operating table and deep humerus during the surgery in the lateral decubitus position. The final 15 participants will have bone marrow aspirated from the PSIS while in the lateral decubitus position on the operating table and deep humerus during the surgery in the lateral decubitus position. Bone Marrow Aspirate will be concentrated at a 12% hematocrit setting independently from each site. One mL of cBMA from each harvest site from each surgery will be removed and sent to the AREF RMC for analysis. The remaining cBMA will be used to augment the rotator cuff repair surgery.

6.1 Surgical Procedure and cBMA Collection:

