The first 15 participants will be placed in the prone position on the operative table for the bone marrow harvest from the PSIS. After bone marrow harvest from the PSIS, the patient will be placed in the lateral decubitus position for the rotator cuff repair. Rotator cuff repair is always performed in either the lateral decubitus position or an upright, seated position called the beach chair position. The final 15 participants will be placed in the lateral decubitus position on the operative table for the bone marrow harvest and the rotator cuff repair. The PSIS harvest will be performed first. The skin will be prepped and draped in sterile fashion over the PSIS. Lidocaine 1% will be used to anesthetize the skin around the incision location. A stab incision will be made in the skin over the PSIS. Two 30 cc syringes and a traditional 11-gauge, 11 cm Jamshidi needle (Ranfac Corporation, Avon, MA, USA) will be pre-rinsed with heparin. The two 30 cc syringes will be loaded with 4 cc of anticoagulant citrate dextrose solution-A (ACDA). The needle will be advanced into the bone marrow cavity 3-4 cm. 30 mL of bone marrow will be aspirated while the needle is withdrawn and rotated with one syringe. The needle will then be reinserted divergently, and another 30 mL of bone marrow aspirated with the second syringe. This method has been described and quantitatively studied with similar harvest to a multiple puncture technique (18). A sterile dressing will be applied. The participant will be re-prepped and draped in standard fashion for shoulder arthroscopy. A diagnostic arthroscopy will be performed, and the rotator cuff tear identified. While

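### Harvest position follows enrolment order (first 15 prone, final 15 lateral), so the secondary prone-versus-lateral comparison cannot be separated from calendar period

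*Protocol*

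**What the plan says.** Section 2 allocates position by sequence: "The first 15 participants will have bone marrow aspirated from the PSIS while in the prone position on the operating table", then "The final 15 participants will have bone marrow aspirated from the PSIS while in the lateral decubitus position on the operating table". Section 6 repeats the rule, and Section 6.1 gives it again for the operative set-up ("The final 15 participants will be placed in the lateral decubitus position on the operative table for the bone marrow harvest"). No randomisation, alternation or concurrent control for position appears.

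The question put to these cohorts is causal. The introduction states that "we aim to determine if patient positioning during PSIS harvest has any effect on the cellular content of collected cBMA". Section 3.2 sets out to "determine if prone verses lateral decubitus participant positioning influences the quantity of harvested cells from the PSIS". Section 4.2 includes in the alternative hypothesis: "Additionally, patient positioning will affect the cellular content of bone marrow from the PSIS".

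Section 10 gives the analysis: "Data will be analyzed for differences between experimental groups (PSIS v. deep humeral harvest, Prone vs. lateral decubitus positions) using 1-Way ANOVA", at p < 0.05 for all measures. No period, order or patient covariate is named. Section 2 also states that both sites are harvested in every surgery and that the humeral harvest is done in the lateral decubitus position in both cohorts.

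**The concern.** Position is a fixed function of enrolment order. All prone harvests belong to the first half of the series and all lateral harvests to the second. Anything that shifts PSIS yield, or its measurement, between the two halves goes into the position contrast, and a one-way ANOVA cannot separate the two.

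The protocol itself suggests how a shift could arise. Its introduction says that yield varies with body mass and aspiration technique, and both patient mix and operator technique can change over a sequential series. A drift could produce a false difference, or it could mask a real one. Position is the whole of the secondary objective and half of both hypotheses, so a positive or a null result would be hard to interpret.

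**Working it through.** **Inputs.** From the protocol: 30 patients, 15 per position in sequence (Section 2); one-way ANOVA at 0.05 (Section 10), which with two groups is the t test. Two-sided testing is assumed. The protocol gives no SD, effect size or power for this comparison, so there is no stated figure to reproduce. Results are in SD units for normal data, and every drift size is an assumption.

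**1. Overlap of position with order.** Mean order is 8 for patients 1–15 and 23 for patients 16–30, a difference of 15. The covariance of the position indicator with order is 0.25 × 15 = 3.75. The SDs are 0.5 and √((30² − 1)/12) = 8.655. So r = 3.75/(0.5 × 8.655) = 0.8665, and the variance inflation is 1/(1 − 0.8665²) = 4.01.

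**2. Linear drift, no true position effect.** A drift of D SD from patient 1 to patient 30 gives a bias of D × 15/29 = 0.517 D.

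| Drift D (SD) | Bias (SD) | Rejection by the 5% test |
|---|---|---|
| 0 | 0 | 5% |
| 0.1 | 0.05 | 5.2% |
| 0.25 | 0.13 | 6.4% |
| 0.5 | 0.26 | 10.6% |
| 1.0 | 0.52 | 26.8% |
| 1.5 | 0.78 | 51.3% |

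The rows for 0.1 and 0.25 come from the noncentral t; those from 0.5 upwards come from 40,000 simulated trials each.

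**3. Step change at patient 16.** The step passes whole into the contrast. Steps of 0.25, 0.5 and 1.0 SD give rejection in about 10%, 26% and 75% of trials.

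**4. Adding a linear order term to the sequential design.**
- Under linear drift, type I error returns to about 5%.
- The standard error rises from √(2/15) = 0.365 (28 df) to 0.365 × √4.01 = 0.731 (27 df).
- The difference detectable with 80% power goes from 1.06 to 2.13 SD, and power for a 1 SD effect falls from 75% to 26%.
- Under a step of 0.5 or 1.0 SD, the mean estimate is still 0.50 or 0.99 SD, so the bias stays.

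**5. Using the humeral sample.** Suppose a 1 SD step at patient 16 acts equally on both sites, with equal variances and within-patient correlation ρ.
- The PSIS-minus-humerus difference, compared between cohorts, removes the step (type I error about 5%). Its SD is √(2(1 − ρ)). Power for a 1 SD position effect is 47%, 61%, 75% or 93% at ρ = 0, 0.3, 0.5 or 0.7.
- Adjusting for the humeral value as a covariate leaves 1 − ρ of the step: 1.0 SD at ρ = 0 and 0.30 SD at ρ = 0.7.
- Neither removes a drift specific to PSIS harvest.

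**6. Randomised alternative.** Permuted blocks (three of 2 and six of 4, giving 15/15) with order in the model were simulated as 1,000 lists × 200 trials per drift. Bias is 0.00 SD and type I error 5.0% at linear drifts of 0.5, 1.0 and 1.5 SD. Power for a 1 SD effect stays at 75%, with mean variance inflation of 1.0006. Without the order term the blocked test is conservative (4.8%, 4.0% and 3.2%).

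**The case against.** The sequential cohorts are openly described, and the protocol never claims that they are randomised. Only a secondary objective is touched. Harvest and processing are well standardised: one site and one laboratory, and the same needle, syringes, anticoagulant volume, PSIS technique, concentrator setting and CBC analyser (Sections 2, 6.1 and 6.2). Small drifts do little harm. The humeral sample, taken in the same position throughout, is a concurrent control that a SAP could use. Changing the theatre set-up once is also simpler than alternating it.

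Much of this stands as context. Standardisation makes a large drift less likely, and the size of any bias is unknown. The protocol orders participants, not surgery dates, so the cohorts could overlap slightly around patients 15 and 16. A PSIS-minus-humerus difference would remove drift common to both sites.

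It does not answer the point. Standardised equipment does not fix patient mix or operator experience. The humeral difference is not planned, covers only shared drift, and has less power than the direct comparison unless the within-patient correlation is at least about 0.5. No analysis can alter an allocation that the protocol has already fixed.

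**Conclusion.** The concern holds, for the secondary objective only. Position is confounded with period by a stated design rule, while the protocol asks a causal question and names a test with no period term. The confounding is certain. Its practical size is not: the inflation to about 11%, 27% or 51% rests on assumed linear drifts of 0.5, 1.0 or 1.5 SD, and at 0.25 SD it is only 6.4%. A later analysis plan can reduce the problem but not fully repair it, because a step at patient 16 that affects PSIS harvest alone cannot be told apart from position. The within-patient comparison of PSIS with humerus is not affected. This should be fixed, and it does not threaten the primary aim.

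**What to change.** **If enrolment has not begun.** In Sections 2, 6 and 6.1, replace the sequential rule with: PSIS harvest position will be allocated 1:1 at random in permuted blocks of 2 and 4 (15 prone, 15 lateral decubitus), revealed after consent. In Section 10 add: the position comparison will include enrolment order (or block) as a term.

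**If enrolment has begun in sequence.** Label the position comparison non-randomised and exploratory. Reword Section 3.2 and Section 4 so that they ask whether yield differs between the prone and lateral cohorts, and draw no causal conclusion. An analysis using the same patient's humeral value may be shown as a sensitivity analysis. Covariate adjustment should not be described as controlling for drift, and a PSIS-minus-humerus difference should be described as removing only drift shared by both sites.

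**Cost.** A 30-line randomisation list, a protocol amendment and, probably, a sentence in the consent form. The patients, the procedures and the number of harvests in each position stay the same, and nothing here favours either position. The downsides are that the theatre set-up varies between cases instead of changing once, and that small blocks at one unblinded site are partly predictable; revealing the allocation only after consent limits the second.
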